D.1. Design and Randomization: Subjects will be drawn from Fetter Health Care Network (FHCN). It is the sole FQHC center in the 4-county area (8 clinics) and provides ~60% of routine AA healthcare in the 4 county area.¹⁰⁷ A support letter from the FQHC network is included. EMR files indicated they have ~2,619 AAs (21-59 yrs old; mean age=45.3yrs) with sole diagnosis of uncontrolled HTN. We will use the 8 practice sites in a 2 arm RCT design (n=192) with clinic as unit of randomization and patient as unit of analysis. All primary healthcare providers across the 8 clinics have agreed to participate if selected. Each clinic has a minimum of 2 primary providers (at least 1 MD and 1 or more NPs and/or PAs per clinic). Thus, 2 providers per site will be recruited. Each will have 12 of their patients recruited (24 per clinic). Given our ~90% participation rate in previous FQHC studies^{25,108,109} and 93% SMASH participation rate, we anticipate no recruitment problems. The Medical University of South Carolina Family Medicine and Internal Medicine clinic population will be an additional recruitment resource if needed.

D.2. Participants: With consideration of the relevant biological variable of gender, we will recruit 192 AA 21-59 yr old uncontrolled HTNs with equal numbers of males and females that meet the following inclusion/ exclusion criteria: 1) SBP ≥ 140 mmHg on most recent clinic visit over last 12 mos and at BP screening and recruitment visits; 2) MPR < 0.85 over last 3 mos; 3) 24-hour SBP ≥ 130 mmHg (HTN cutoff) to help rule out white coat HTN.^{76,110} SBP used as selection variable since most AA HTNs < 60 have systolic or combination systolic/ diastolic HTN and for most patients, controlling SBP also results in DBP control;^{27,111,112} 4) no other known chronic diseases (e.g., diabetes, chronic kidney disease (GFR < 50 ml/1.73 m²/min), cancer, renal dialysis, heart attack, coronary artery bypass, arterial stent, substance abuse (e.g., > 21 drinks/week), psychiatric illness, Beck Depression Inventory¹¹³⁻¹¹⁵ > 13 , able to speak, hear and understand English; take own BP and meds; 6) owns smart phone with current data plan; 7) primary care MD's assent patient able to participate and 8) no planned pregnancy or vulnerable population (e.g., pregnant or nursing women, prisoners).

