Cochran-Mantel-Haentzel chi-square tests of differences in % of patients being >0.90 med adherent and % of patients within JNC8 guidelines for BP control (<140/90 mmHg) at the 6 month visit (primary endpoint) between the two groups (SMASH; enhanced SC). Type I error rate was 0.05 (two-sided). Sample size was adjusted to account for the cluster randomization scheme, using variance inflation factor (VIF) method.¹⁴⁸ Power and sample size estimates were performed for within-clinic sample sizes of 22 subjects for 4 clinics per group, assuming ICCs ranging from 0.0 to 0.05. The ICC from our feasibility trials for primary outcomes of electronic med tray based MA and SBP was estimated at 0.04. For an ICC of 0.04 the proposed sample size of 22 per clinic and 4 clinics per group provides at least 90% power to detect a difference in the assumed 6-month MA/BP control rates between the 2 groups (difference of $\geq 30\%$ between SMASH and SC based on feasibility trials' results).^{22,23,25,26} For the proposed study, for calculation of the VIF we used the conservative absolute ICC value of .04 for a final sample size 176. We inflated that by 10% (N=192) to account for greater than expected attrition across the trial. Conservative estimates for expected MA (or BP control) proportions were used for power calculations; proportions observed in our SMASH feasibility studies were 89% vs. 0%, N=19 for MA based upon MedMinder^{22,23} and for resting SBP, an average of 90% vs. 10% for the three trials lasting 3 and 6 months and the recent 12-month follow-up (n=19,²² n= 22,²⁵ n= 24,²³ n=19,²²). For secondary continuous outcomes of 24-hr BP (and MPR derived MA scores) for longitudinal analyses [assuming 4 intervention time points (months 3, 6, 12, and 18), level of significance = 0.05 (two-tailed), correlation among repeated measures (ICC ≤ 0.5)], we will have 90% power to detect a 0.48 standardized effect size (i.e., Cohen's d effect size). A standardized effect size of 0.48 sd is equivalent to a raw effect size ranging from 2.4 to 4.3 mmHg (raw scale units) for difference in SBP change from baseline between the groups for a range of sd from 5.0 to 9.0 mmHg, based upon our SMASH feasibility data.^{22,23,25,26} For resting DBP based upon our SMASH findings, this equates to a difference of 1.3 to 3.3 mmHg assuming sd ranging from 2.0-5.0 mmHg. SMASH findings for the tray derived monthly MA scores revealed a difference in MA score changes between the groups from baseline to 3 month of 28% (sd=6.2).^{22,23} Assuming similar adherence in both groups through the 6-month trial, we will have at least 94% power to detect differences in adherence change scores as small as 10% (with sd up to 15).

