D.10. Quantitative Analyses: AIM1 Primary outcome measures are % of subjects with >0.90 MA from MedMinder and % within JNC8 clinic resting BP guidelines (<140/90 mmHg). Secondary analyses will assess resting & ambulatory BP levels (e.g., 24-hr, daytime/nighttime BP level changes) & MA indices (i.e., MPR score changes). Intent-to-Treat (ITT) sample analyses will be used along with multiple imputation methods for missing end-of-study outcomes.^{149,150} To assess relationships between intervention outcomes and intervention status (SMASH or SC) at end of the active trial period (6-mo visit, primary endpoint), two-sided Cochran-Mantel-Haentzel chi-square tests for unadjusted differences in proportions will be used. Adjusted differences in proportions at the 6-mo visit will be compared using logistic regression. To assess relationships over time, we will use a generalized linear mixed models (GLMM; generalized estimation equation [GEE]-type models) analytic model with group (SMASH vs SC) & time (3, 6, 12 & 18 months) included as fixed effects and FQHC practice site as a random effect to account for clustering within FQHC practice site/MD.¹⁵¹⁻¹⁵³ In the first set of models, baseline measurement of the dependent variables (e.g., MA or BP levels) will be included as adjustment variable. The test of primary interest is F-test for the treatment x time interaction, which will reflect a difference in change between the 2 groups over the study. If a statistically significant treatment x time

interaction is found, we will obtain odds ratios for SMASH vs SC groups at each of the study time points.

A mixed effects model (MEM) will be used to compare the primary continuous outcome measures (e.g., tray or MPR derived MA scores or BP levels) for the two groups over the study period. Modeling will be carried out as described above. We will estimate resting and 24-hr BP changes and MA (MPR) changes for each subject over the trial (baseline, 3, 6, 12 & 18 months) and the within subject longitudinal trajectories (e.g., slopes) and summarize as the mean longitudinal trajectory within each group. ICCs and variance estimates will be obtained of efficacy outcomes and covariance structure of the longitudinal scores for determination of sample size (and hence adequate power) for a future effectiveness RCT.

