Cost-effectiveness analyses will be run using established methodology for economic evaluation of electronic drug monitoring for MNA.¹⁵⁴ Data will be collected on incremental direct and time cost SMASH program adds to enhanced SC for facilitating MA and BP control. This includes personnel costs for referral & BP/ MA screening, all supplies and equipment used (MedMinders, BP devices, smart phones/ data packages) and costs of additional meds beyond SC. Value of project manager's time will be included in attending to patient assistance calls, verification of out of range BPs, etc. Sensitivity analyses will estimate cost changes related to different types of personnel time needed to perform her tasks. We will define benefits as difference in cost of health services use and lost worked days between SMASH and SC groups. We will compare costs of emergency department (ED), outpatient and hospital visits during the 6-month trial and most importantly, the 12 months following trial completion. We will use estimates from the Healthcare Cost and Utilization Project¹⁴⁵ for ED and hospitalization and the Medical Expenditure Panel Survey¹⁴⁴ (for outpatient and individual out-of-pocket costs) to value healthcare use costs in each group. Thus, healthcare costs will be evaluated at institutional provider, third party payer and individual level and all costs adjusted using inflation adjustment from Bureau of Labor Statistics.¹⁵⁵ We will estimate cost of lost worked days during the 6-mo trial and 12-mo follow-up and reported baseline income. We will assess differences in means, medians and quartiles based on distribution of the variables. As we did in another telehealth project, we will use GLM with appropriate distribution to examine association of SMASH with patient level healthcare costs and patient lost income adjusting for patient demographics and comorbidities.¹⁵⁶ We will conduct sensitivity analyses by estimating different healthcare costs and income models while adjusting for clinical outcomes (e.g., % with JNC8 BP control; % with 24-hr BP control). We will do the same for healthcare utilization and lost workdays using a count model (Poisson or Neg Bin if over dispersion occurs or zero-inflated if many zeros are present). We will perform a comparison of SMASH cost with changes in clinical outcomes to provide cost-effectiveness ratios for clinical outcomes.

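### The exploratory cost, lost-income, utilisation and lost-workday models (D.10, Aim 3) carry no clinic term although eight clinics are randomised, so their p-values will be too small and intervals too narrow if these outcomes vary by clinic

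*Combined protocol and SAP*

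**What the plan says.** D.1 sets up a cluster design "with clinic as unit of randomization and patient as unit of analysis". There are eight sites, four per arm.

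For the Aim 1 longitudinal model, D.10 includes "FQHC practice site as a random effect to account for clustering within FQHC practice site/MD". The Aim 2 paragraph and the Aim 3 laboratory paragraph each refer back to that modelling. The responses to critiques in the Introduction to Revised Application also say, in general terms, that clinic will enter the analytic model as a random effect, and they point to D.10.

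The economic paragraph of D.10 (Aim 3) stands apart. For costs and lost income it says "we will use GLM with appropriate distribution to examine association of SMASH with patient level healthcare costs and patient lost income", following another telehealth project, with patient demographics and comorbidities as adjusters. Utilisation and lost workdays are handled in the same way with a "count model (Poisson or Neg Bin if over dispersion occurs or zero-inflated if many zeros are present". The paragraph names no site effect, GEE or cluster-robust variance and does not refer back to Aim 1.

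**The concern.** When clinics are randomised, the arm comparison has to be judged against variation between clinics. A GLM or count model with patient covariates only judges it against variation between patients. Moving from Poisson to negative binomial does not repair this: the extra dispersion is still patient-level and the patients are still taken as uncorrelated. A difference between clinics that has nothing to do with SMASH can then appear as an arm effect on cost, visits or workdays.

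Clinic differences are plausible here. The Introduction reports that the lead site has 7.3 providers and about 45% of patient encounters, while the other seven sites average 2.4 providers. The stake is a cost or utilisation difference reported with too much certainty. Within the cost comparison, the plan gives most weight to the 12 months after the intervention.

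**Working it through.** **Inputs.** D.1: "Each will have 12 of their patients recruited (24 per clinic", so 96 per arm. D.8: power was worked out for "within-clinic sample sizes of 22 subjects for 4 clinics per group", so 88 per arm. D.8 on the ICC: "The ICC from our feasibility trials for primary outcomes of electronic med tray based MA and SBP was estimated at 0.04", with calculations "assuming ICCs ranging from 0.0 to 0.05". Alpha is 0.05 two-sided, which D.8 also states for the Aim 3 outcomes, naming cost effectiveness. No ICC is given for cost, utilisation or lost workdays, so the D.8 values serve as assumptions.

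**Reproducing D.8, Aim 1.** VIF = 1 + (22 − 1) × 0.04 = 1.84. Effective n per arm = 88/1.84 = 47.8. For 40% against 10% (the pilot control rate for BP control plus 30 points), power is 0.936, in line with the stated 90% or more. N = 8 × 22 = 176, and 176 × 1.10 = 193.6, against 192. The sponsor's allowance for clustering is therefore clear for the primary outcomes.

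**Reproducing D.8, Aims 2 and 3.** The text gives 80% power for 0.53 SD with an independent-sample t-test. That needs about 56 independent patients per arm. With 88 to 96 independent patients per arm, power would be 0.94 to 0.96. The implied design effect is 88/56 = 1.57 to 96/56 = 1.71, so the implied ICC is 0.57/21 = 0.027 to 0.71/23 = 0.031.

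**Error rate if clinic is left out.** Actual two-sided error = 2 × [1 − Φ(1.96/√VIF)], with VIF = 1 + (m − 1) × ICC:

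| ICC | VIF (m = 22 / 24) | Actual error (m = 22 / 24) | Ratio to 5% |
|---|---|---|---|
| 0 | 1.00 / 1.00 | 5.0% / 5.0% | 1.0 |
| 0.01 | 1.21 / 1.23 | 7.5% / 7.7% | 1.5 |
| 0.02 | 1.42 / 1.46 | 10.0% / 10.5% | 2.0 to 2.1 |
| 0.03 | 1.63 / 1.69 | 12.5% / 13.2% | 2.5 to 2.6 |
| 0.04 | 1.84 / 1.92 | 14.8% / 15.7% | 3.0 to 3.1 |
| 0.05 | 2.05 / 2.15 | 17.1% / 18.1% | 3.4 to 3.6 |

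Half of each error falls in the direction favouring SMASH: 7.4% to 7.9% against 2.5% at ICC 0.04.

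**Simulation check.** The setting was 8 clinics of 24, no arm effect, no covariates, and 2,000 to 3,000 runs per case. Assumed shapes were costs with CV 1.5 and counts with mean 1 and dispersion 1. At ICC 0.04 the models without clinic rejected in about 16% of runs (gamma-log GLM, negative binomial and normal alike). At ICC 0.05 they rejected in 18.5% (normal) to 21% (gamma and negative binomial), slightly above the formula. A t-test on clinic means with 6 df stayed between 4% and 6% at every ICC tried.

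**Cost of doing it properly, at ICC 0.04.** Interval width relative to a model that ignores clinic is √VIF × 2.447/1.960: 1.69 for m = 22 and 1.73 for m = 24. The standard error in SD units is √(2 × 1.84/88) = 0.204 or √(2 × 1.92/96) = 0.200. Power at 0.53 SD on 6 df is then 58% to 60%, and the difference detectable with 80% power is 0.67 to 0.69 SD.

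**The case against.** The plan never says that patients will be treated as independent in the economic models. A reader might infer that from the missing clinic term, but it is an inference from silence. The Introduction's statement about a clinic random effect points to D.10, which contains the economic paragraph, and how the earlier telehealth project handled clustering cannot be seen from the documents. The 0.53 SD figure in D.8 covers cost effectiveness by name and seems to include a design effect, which suggests that clustering was in mind. All of this stands, and it rules out saying that the plan chose an independence analysis.

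It does not supply the missing term. Within D.10 the site random effect belongs to the longitudinal model, and the plan says so where it reuses that modelling. The economic paragraph instead names a different model and lists its adjusters. A power figure does not fix an analysis model.

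Two further limits also stand. ED, hospital and outpatient use is valued from external estimates, so clinic price differences would not enter those costs, and covariate adjustment may absorb part of the clinic variation. What matters is the residual ICC, which is unknown. The outcomes are also exploratory, and the economic paragraph sets no significance threshold or decision rule.

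**Conclusion.** The point holds as an omission with a calculable consequence. Followed literally, the economic paragraph gives standard errors that are too small whenever the clinic ICC for these outcomes exceeds 0. Over ICC 0 to 0.05 with equal clinics of 22 to 24, actual error is about 5% to 18%, or 1.0 to 3.6 times nominal.

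A reader might take away a flat threefold inflation. The documents support that only if the ICC for adherence and systolic pressure also applies to costs and use, which they do not say. At ICC 0 there is no inflation.

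A reader might also infer that adoption of SMASH hangs on this cost result. Section A.5 says only that the package needs a fully powered trial if it is to be adopted and eventually reimbursed, and a further effectiveness trial is planned. The matter deserves correction before analysis, in proportion to an exploratory aim.

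**What to change.** In D.10, Aim 3, state that the arm effect in the cost, lost-income, utilisation and lost-workday analyses, including the sensitivity models, is tested against between-clinic variation with about 6 df. Name one main method in advance:

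- covariate-adjusted clinic-level summaries compared on 6 df; or
- a permutation test over the 70 possible 4 v 4 allocations, which also serves medians and quartiles; or
- a practice-site random intercept with a small-sample correction, where the model is stable. With eight clinics this may fail for zero-inflated models, and it does not apply to medians and quartiles.

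Base any intervals for cost differences and cost-effectiveness ratios on the same clinic-level variance.

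This is a change of wording and model specification, with no new data. The price is precision: at ICC 0.04, intervals about 1.7 times as wide and power at 0.53 SD of about 58% to 60% rather than the stated 80%. The permutation test is also coarse. Its smallest two-sided p-value is 2/70 = 0.029 and the next is 4/70 = 0.057, so only the most extreme split reaches 5%.

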D.3. Recruitment: Proposed procedures were successful in our SMASH pilot trials.^{22,23,25,26} Practice sites will prepare a list of eligible patients and [name] (project manager) will contact them, explain the study and, if interested, schedule the screening/recruitment visit. As part of **design rigor**, other MUSC staff will conduct the evaluations below using established protocols. They will remain blinded as to patients' group status throughout study (i.e., baseline, 3 and 6 months, and post-trial follow-ups at 12 and 18 months). Subjects who develop any comorbidities over the study period will remain in the trial and all meds will be monitored.

D.3.a. Resting and 24-hr BP screening: After obtaining informed consent, resting BP protocol will be conducted using our established protocol with the previously validated BpTRU device.¹¹⁶ **If SBP ≥ 140 mmHg** from last 2 readings of 10 min protocol, **they will continue with screening:** height, weight and waist/hip ratio will be recorded (BP and anthros protocols in Appx. 5 and 6). Based on their preference, a set of **questionnaires will be given** orally or read on their own (see D.6 Measures; Table 3; copies in Appx. 7-21). They will have the option of using their smart phone, TACHL provided tablet, or paper copy version. They will **then wear** the previously validated¹¹⁷ **SpaceLabs 90207 BP monitor for 24 hrs** using our established protocol.¹¹⁸⁻¹²⁰ Protocol and criteria for acceptable readings, generating 24-hr averages, etc. are in Appx. 22. **Only those with 24hr SBP ≥ 130 mmHg will proceed to the MNA identification phase below.**

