
will have a wealth of data to address important issues not detailed which will guide our future work. For example, we will use triangulation of Morisky MA self-report scale, MPR, pharmacy record information and MedMinder data to develop an effective algorithm for MA measurement.

PROTECTION OF HUMAN SUBJECTS

This Human Subjects Research meets the definition of a clinical trial.

1. Risks to Human Subjects

a. Human Subjects Involvement, Characteristics, and Design

This will be a two-arm RCT design that will assess efficacy of the SMASH mHealth program compared to an enhanced standard care (SC) program. Participants will be drawn from Fetter Health Care Network (FHCN), the sole FQHC center in the 4-county area (Charleston, Dorchester, Colleton and Berkeley counties). The Medical University of South Carolina Family Medicine and Internal Medicine clinics will be available if needed for recruitment of participants. Collectively, this offers a unique opportunity to recruit underserved, at risk patients without extensive screening protocols. We will recruit 192 AAs with uncontrolled HTN (no other comorbidities) and MNA according to the inclusion and exclusion criteria below and the methods described in Section D.2. Participants. The Fetter Health Center Information Technology Department will provide a list of potentially eligible patients to the SMASH project manager, [name]. She will make the initial phone contact with potential subjects. She will inform them about the study and that they will have an equal chance of being randomized to either the enhanced health education (i.e., enhanced standard care [SC]) or SMASH cohort if they are found eligible at the conclusion of the screening period. Following a successful BP screening (SBP ≥ 140 mmHg), a battery of questionnaires are completed and then 24-hour BP monitoring will occur. Likelihood of white coat hypertension in these patients is low.^{30,75,76} We found no case of white coat hypertension in the FQHC feasibility trial involving AAs. If the participant's 24 hour SBP is ≥ 130 mmHg, he/she will proceed to the next phase of screening involving use of the Maya MedMinder for one month with reminder signals deactivated. If MA score $< .85$, they will again complete the baseline clinic BP evaluation and 24-hr BP monitoring to reconfirm uncontrolled SBP HTN.

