4. uncontrolled HTN (SBP ≥ 140 mmHg) based upon last clinic visit within previous 12 months, initial clinic screening and subsequent recruitment evaluation following one month med intake screening with score of $< .85$;

5. 24-hour SBP \geq 130 mmHg on clinic screening and subsequent recruitment evaluation;
6. Ability to speak, hear and understand English;
7. Able to take their own BP and self-administer medications;
8. Owns smart phone with data plan;
9. Primary care provider's assent that patient is able to participate

Exclusion Criteria:

1. No other known chronic disease (e.g., chronic kidney disease (GFR $<$ 50 mL/1.7 m²/min; diabetes (type one or two); renal dialysis ; cancer diagnosis or treatment in past 2 years; prior cv event such as heart attack, congestive heart failure, arterial stent, coronary artery bypass graft ; psychiatric illness
2. Beck Depression Inventory score $>$ 13
3. Ongoing substance abuse (e.g., $>$ 21 drinks/week);
4. Planned pregnancy;
5. Vulnerable populations such as pregnant or nursing women, prisoners, and institutionalized individuals.

Healthcare Team Focus Groups: The 8 primary providers and their nurse managers whose 4 practice sites are randomly selected to deliver SMASH will be eligible to attend a focus group after all patients have completed the final follow-up. All participants will provide written informed consent before taking part in the focus groups and we anticipate that, as before, all healthcare team members will participate. Due to the nature of this sample, a targeted/planned enrollment recruitment table based on gender, race, or ethnicity was not developed.

b. Sources of Materials

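### The cost models in Aim 3 adjust for BP control, and possibly for new comorbidities, so they do not estimate the between-group cost difference that the plan defines as the benefit

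*Combined protocol and SAP*

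**What the plan says.** The cost-effectiveness paragraph of D.10 (AIM 3) first fixes the quantity of interest: "We will define benefits as difference in cost of health services use and lost worked days between SMASH and SC groups". Costs are compared over the 6-month trial and, "most importantly, the 12 months following trial completion".

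Three layers of analysis follow:

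- A comparison of means, medians and quartiles between groups.
- A GLM relating SMASH to patient-level healthcare costs and "patient lost income adjusting for patient demographics and comorbidities".
- Sensitivity analyses that re-estimate the cost and income models "while adjusting for clinical outcomes (e.g., % with JNC8 BP control; % with 24-hr BP control").

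The same is then promised for healthcare utilisation and lost workdays, using count models. Finally, SMASH cost is compared with changes in clinical outcomes to give cost-effectiveness ratios.

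On who enters and who stays:

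- Protection of Human Subjects, 1.a: "We will recruit 192 AAs with uncontrolled HTN (no other comorbidities) and MNA".
- Exclusion Criteria, item 1: "No other known chronic disease". D.2 has the same restriction, and the Inclusion Criteria allow prescribed medication for hypertension only.
- D.3: "Subjects who develop any comorbidities over the study period will remain in the trial".

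**The concern.** A model that conditions on something the intervention changes no longer estimates the whole effect of the intervention. It estimates the part that does not pass through that variable, and only if nothing unmeasured drives both the variable and the outcome. BP control is one of the two primary outcomes, and better control is how SMASH is meant to reduce emergency, outpatient and hospital use. Comorbidities that appear during follow-up are also a possible route, since the Narrative expects the programme to lower the risk of future comorbidities once effectiveness has been shown in later trials.

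What is at stake is interpretation. A sensitivity analysis should ask the same question under different assumptions, whereas these models ask a different one. If BP control drives the savings, the adjusted coefficient will shrink towards zero, and a reader could take that as a sign that the saving is not robust when it shows only that the mechanism works as intended.

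**Working it through.** The plan gives no figure to reproduce here, so the check has two parts: when the covariates can vary, and what adjusting for them does.

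**1. When the covariates can vary**

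*BP control.* Inclusion Criteria 4 and 5 require resting SBP of at least 140 mmHg and 24-hour SBP of at least 130 mmHg at screening and again at the recruitment evaluation. Control means below 140/90 and below 130/80. No enrolled patient is controlled at entry, so this covariate varies only after enrolment.

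*Comorbidities.* Other known chronic disease is excluded at entry, and patients who develop comorbidities stay in. The term is therefore close to constant at baseline and would vary mostly through conditions recorded later. The plan does not say when it is measured.

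**2. Adjusting for BP control: arithmetic**

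Let D be the difference in BP-control rates, d the extra cost of an uncontrolled patient, and s the saving that does not act through BP. In a linear model:

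- total effect = −s − D × d
- BP-adjusted effect = −s
- share removed = (D × d) / (s + D × d)

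D = 0.30 is the planning difference in D.8 (at least 30 percentage points). The values of d and s are assumptions, because the documents give none.

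| d | s | Total effect | BP-adjusted | Share removed |
|---|---|---|---|---|
| 1000 | 0 | −300 | 0 | 100% |
| 1000 | 300 | −600 | −300 | 50% |
| 1000 | 600 | −900 | −600 | 33% |
| 4000 | 300 | −1500 | −300 | 80% |
| 4000 | 600 | −1800 | −600 | 67% |

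**3. Adjusting for comorbidity: arithmetic**

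Assume BP control of 30% in SC and 60% in SMASH, d = 1000, s = 0, and an incident comorbidity that costs 3000 and has 10% risk, halved by BP control.

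- SC risk: 0.7 × 0.10 + 0.3 × 0.05 = 0.085
- SMASH risk: 0.4 × 0.10 + 0.6 × 0.05 = 0.070
- Cost through comorbidity: 0.015 × 3000 = 45
- Total effect: −(0.30 × 1000) − 45 = −345
- Share through comorbidity: 45 / 345 = 13%

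**4. Simulation**

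A simulation used 400,000 subjects, gamma-distributed costs and additive linear regression. All cost and comorbidity inputs are assumed. The SMASH coefficients were:

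| Scenario | Unadjusted | Adjusted for comorbidity | Adjusted for BP control |
|---|---|---|---|
| As in part 3 | −343 | −298 (13% removed) | about 0 |
| As above, plus direct saving of 300 | −643 | −593 (8% removed) | −295 |
| As in part 3, plus an unmeasured common cause of BP control, comorbidity and cost | −344 | −284 (17% removed) | +185 |
| Comorbidity costs 6000; risk 20%, cut to 6% by BP control | −540 | −271 (50% removed) | about 0 |
| SMASH does not change comorbidity | −295 | −297 (none removed) | about 0 |

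The +185 matters beyond its size. Once BP control is in the model, a shared unmeasured cause can reverse the sign, so the error need not be simple attenuation.

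**The case against.** Several points on the other side stand.

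- **The total effect is not lost.** The comparison of means, medians and quartiles is unadjusted and estimates it.
- **The BP-adjusted models are labelled as sensitivity analyses.** How costs compare at a given BP status is a fair secondary question. However, the plan does not present these models as answering it, and the mediation and structural equation work elsewhere in D.10 concerns adherence and BP control, not cost.
- **The aim is exploratory.** No primary or secondary conclusion depends on it.

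Three stronger readings are tempting, and the documents do not support them.

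- *A reader might infer that comorbidity can only be a post-enrolment variable.* Only known disease is excluded, and with limits: GFR below 50, cancer in the past 2 years, and a Beck score above 13. Baseline bloods could reveal unrecognised conditions. The Exploratory Moderator Analyses say explicitly when new comorbidities are meant; the cost paragraph does not. The timing is unstated.
- *A reader might infer that the cost-effectiveness ratio has a biased numerator.* The ratio sets SMASH cost against clinical outcomes, and programme cost is built from personnel, devices, phones and additional medication. Nothing says that an adjusted coefficient enters it.
- *A reader might size the problem from the pilot emergency-department savings in C.1.4.* Those are group totals: 4 × $5,923 = $23,692 for SMASH (7 to 3 visits) and 1 × $5,923 for SC (13 to 12). They do not scale a patient-level model, and the documents do not give the share acting through BP control or comorbidity.

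**Conclusion.** The point holds as a low-severity matter of model specification. The BP-adjusted models for cost, income, utilisation and lost workdays do not estimate the benefit as the plan defines it. They should not be read as testing whether that benefit is robust. The comorbidity term in the main GLM carries the same risk to the extent that it captures conditions recorded after enrolment.

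The size cannot be derived from the documents. The illustrations suggest that it could be large for BP control, while for comorbidity it may be small and is zero if SMASH does not alter comorbidity within the 18 months. These ranges rest on assumed costs and risks and on the 30-point planning difference.

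**What to change.** Amend the cost-effectiveness paragraph of D.10 in three places:

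1. In the main cost, income, utilisation and lost-workday models, adjust only for variables measured at baseline: demographics, baseline SBP, any comorbidity recorded at baseline, and prior utilisation if it is held. Limiting the comorbidity term to baseline is enough; it need not be deleted.
2. Report the SMASH coefficient from these models as the total effect, and use that estimate wherever healthcare cost differences enter the cost-effectiveness results.
3. Relabel any model containing BP control or new comorbidities as an exploratory mediation analysis, and state that it does not estimate the total cost effect.

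This is a free improvement: wording only, with no effect on sample size, visits or the primary analyses. The one possible extra is extraction of prior utilisation, which is optional.
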